11.4.5 Analyses of quality of life/health economics variables

The analysis of QOL data will be performed on the QOL population. Baseline is defined as the visit 1 (week 0) evaluation.

Data on the 5 items

The responses of each EQ-5D items will be presented by visit for each treatment arm using tables. The tables will contain information on the frequency and proportion of the population reporting level 1 (no problems), level 2 (some problems) and level 3 (extreme problems) per item, by treatment arm.

Scoring the EQ-5D health states

The 5 dimensional 3-level system will be converted into a single index utility score: values for the 243 theoretically possible health states defined by the EuroQol classification are calculated using a regression model (36). The single index utility score will be described by visit and treatment arm.

Absolute change from Baseline to the following time points

The absolute change of health-related QOL (single index utility score) from baseline to following time points will be described in the QOL population for each treatment arm using the same MMRM model as for the continuous secondary efficacy endpoints of lipids anticipated to have a normal distribution and collected at Week 0, Week 4, Week12, Week 24 and Week 36 with corresponding baseline value as covariate.

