8.3 BLINDING PROCEDURES

8.3.1 Methods of blinding

This study is an open-label design and the IMP administration during the study period will be under un-blinded manner. Despite the un-blinded IMP administration, assessment for the primary and key secondary efficacy endpoints will be conducted in the central reading laboratory based on objectively collected imaging data blinded to study treatment arms.

The study team or delegate must not summarize the primary efficacy endpoint by treatment arm, but may review the descriptive statistics of the primary efficacy endpoint by pooling the data from both arms.

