8.4 METHOD OF ASSIGNING PATIENTS TO TREATMENT GROUP

Sponsor will provide the randomization scheme to the registration center. Then, the registration center will generate the patient randomization list.

The IMP (i.e., Praluent[®]) is provided in open-label boxes.

Patient identification (patient number) is composed of 9-digit number containing the 3-digit country code, the 3-digit study site code, and the 3-digit patient chronological number.

Before randomizing a patient, the Investigator/sub-Investigator or designee will have to contact the registration center. A randomized patient is defined as a patient who has been allocated to a randomized treatment and recorded in the registration center database, regardless of whether a study drug is used or not. A patient cannot be randomized more than once in the study. If the IMP is used without contacting the registration center, patient will be considered as not randomized and withdrawn from the study.

At the randomization visit, patients will be randomized to either alirocumab arm or SoC arm at a ratio of 1:1 with permuted-block randomization using the registration center. Randomization will be stratified by 'statin therapy' or 'not on statin therapy' at the ACS onset.

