10.1.1.1 Study site visit

10.1.1.1 Randomization visit (Visit 1 / Week 0 / D1)

Blood sampling should be completed before IMP administration.

This visit includes:

- On-site visit.
- Complete and collect written informed consent for the study by the randomization visit. Patient number will be allocated by the registration center. The patient number is composed of a 9-digit number containing the 3-digit country code, the 3-digit center code, and the 3-digit patient chronological number (3-digit patient chronological number is 001 for the first patient screened in a center, 002 for the second patient screened in the same center).

Note: The written informed consent can be obtained any time between ACS diagnosis and the randomization visit (see [Section 1.2](#)).

- Confirm inclusion and exclusion criteria.
- Collect information about therapeutic intervention such as ACS culprit vessels, IVUS imaging locations (refer to [Section 17](#), Appendix D for vessel locations), and types of stent placed at the PCI (BMS or DES).

- Contact the registration center to notify the patient enrollment. After the final confirmation of inclusion and exclusion criteria at the registration center, the arm to which the patient randomized to is communicated.
- Demographics (age, gender, race, ethnicity).
- Collect contact information (address, email, home and cell phone numbers) of the patient, patient's family members, and patient's primary care physician / cardiologist.
- Patient's medical and surgical history (including menopausal status, and family history), alcohol habits, smoking habits, lipid parameters including LDL-C used for the study eligibility, and HbA1c.
- Collect patient's history of CV disease.
- Record use of LMT including statins and prescription or over-the-counter non-statin LMTs within 1 month prior to Visit 1.
- Record of all concomitant medications including CV medications.
- Collection of adverse events including CV events (if any).
- Collection of results of hepatitis B virus surface antigen and antibody tested at the time of ACS diagnosis and PCI.

Note: If the hepatitis B virus surface antigen and antibody titers are not checked, they must be measured prior to the randomization visit and the results must be recorded at the randomization visit (see [Section 7.1](#)).

- Physical examination including vital signs: heart rate and sitting SBP and DBP.
- Body weight and height.
- EQ-5D patient questionnaire.

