- Serum and urine pregnancy tests (women of childbearing potential [WOCBP]).
- Confirm and record compliance with background LMT regimen including NIMPs.
- Fasting blood sample listed below will be collected and measured.
- Hematology and chemistry.
 - TC, calculated and directly measured LDL-C, HDL-C, TG, non-HDL-C (central laboratory).
 - Apo B, Apo A-1, Apo B/Apo A-1, Lp(a) (central laboratory).
 - HbA1c (central laboratory).
 - hs-CRP (central laboratory).
 - Hepatitis B virus antibody (Hepatitis B virus total core antibody is tested at the central laboratory).
 - Hepatitis C virus antibody titer (central laboratory).

Note: Additional blood samples can be obtained for measurement of above listed items and others at the study site by Investigator's judgment as needed.

- If the patient's eligibility (and fasting status) is confirmed, contact the registration center for randomization. The Investigator/sub-Investigator must not administer IMP without notifying the registration center.
- When the Investigator confirms the patient is randomized to the alirocumab arm and has completed fasting blood sample collection and assessments of all evaluations planned at this randomization visit (Visit 1), the first Praluent® injection will be performed at the study site following the patient injection instruction.
- The patient should be observed for at least 30 minutes after Praluent® administration.
- If patient is randomized to the SoC arm, ongoing LMTs will be continued unless modification of LMTs is made by the Investigator's medical judgment.
- For the patient who is randomized to the alirocumab arm, an appointment will be given for next Praluent® administration visit (Week 2 / D15).
- For the patient who is randomized to the SoC arm, an appointment will be given for next on-site visit (Visit 2 / Week 4 / D29). The patient should be instructed to visit the study site in the morning under fasting conditions, which is defined as an overnight fasting no less than 8 hours that consist of no food or liquid intake, other than water unless exception made by Investigator's medical judgment.
- Transfer IVUS imaging data to the central reading laboratory.

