11.4.4 Analyses of other endpoints

All analyses for other endpoints will be performed on the safety population. The baseline value is defined as the last available value before randomization.

The number and percentage of patients with 2 consecutive calculated LDL-C <25 mg/dL and calculated LDL-C <15 mg/dL, respectively, will be provided by treatment arm. The time interval between 2 consecutive calculated LDL-C should be spaced out by at least 21 days.

Exploratory variables defined in [Section 9.3](#) will be summarized by time points for each treatment arm. For hs-CRP, the incidence of PCSA at any time during the TEAE period will be also summarized by treatment arm using descriptive statistics.

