#### **2.4.7 Analyses of quality of life/health economics variables**

The analysis of data from EQ-5D instrument will be performed on QOL population. Baseline is defined as the visit 1 (Week 0) evaluation. Analysis window for efficacy parameters will be used to assign time points (see [Section 2.5.4.2, Table 4](#)).

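### The EQ-5D baseline is tied to Visit 1 but not to the time before randomization, so the plan permits a baseline recorded after the arm is known

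*Protocol*

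**What the plan says.** **Baseline rule.** Protocol 11.4.5: "Baseline is defined as the visit 1 (week 0) evaluation". SAP 2.4.7: "Baseline is defined as the visit 1 (Week 0) evaluation". Neither adds that the evaluation must come before randomization. Protocol 9.3.3 likewise measures change in the index score from the Week 0 visit.

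**When allocation happens.** Protocol 8.4: "At the randomization visit, patients will be randomized to either alirocumab arm or SoC arm at a ratio of 1:1".

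**Order within Visit 1 (Protocol 10.1.1.1).** An early bullet has the site call the registration center to notify enrolment. After a final eligibility check, "the arm to which the patient randomized to is communicated". The EQ-5D bullet comes later. Blood sampling follows, and then: "If the patient's eligibility (and fasting status) is confirmed, contact the registration center for randomization". The first injection is given once the investigator has confirmed the alirocumab allocation and the patient "has completed fasting blood sample collection and assessments of all evaluations planned at this randomization visit (Visit 1").

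**Blinding and collection.** Protocol 8.3.1: "This study is an open-label design and the IMP administration during the study period will be under un-blinded manner". The blinded assessment described there covers the primary and key secondary (IVUS) endpoints. Protocol 10 assigns EQ-5D collection to the investigator or a designee, and footnote l of the flow chart (Protocol 1.2) describes it as an interview.

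**Baseline rules elsewhere.** Protocol 11.4.4: "The baseline value is defined as the last available value before randomization". That section also covers the variables of Section 9.3, and EQ-5D is 9.3.3. SAP 2.1.1 sets the same default except where another rule is given. SAP 2.1.3 ties the lipid baseline to the date and time of randomization.

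**Use of the value.** The utility change from baseline is analyzed by MMRM with treatment group and treatment-by-time terms. Baseline utility is a covariate and also has a time interaction (SAP 2.4.7).

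**The concern.** EQ-5D is the trial's patient-reported outcome, and one of its dimensions is anxiety/depression. A patient who has just learned the allocation may answer differently from one who has not. An interviewer who knows the arm may also influence the answers.

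Randomization balances a baseline covariate only if the covariate is fixed before allocation. If it is recorded afterwards, part of a response to the allocation can sit in the baseline, and the model then adjusts for it. The between-arm utility contrast would no longer be measured from a pre-randomization starting point. It is also odd that lipids, which are far less open to knowledge of the arm, have the stricter timing rule.

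**Working it through.** The documents give no figure to reproduce here. The check has two parts: the sequence in the text, and the size of any bias under stated assumptions.

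**1. Does any rule place the EQ-5D before allocation?**

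| Rule | Where | Does it bind the EQ-5D before allocation? |
|---|---|---|
| Visit 1 evaluation is baseline | Protocol 11.4.5, SAP 2.4.7 | No; allocation is at the same visit |
| Arm communicated after the enrolment call | Protocol 10.1.1.1 | No; listed above the EQ-5D |
| Call for randomization | Protocol 10.1.1.1 | Listed below the EQ-5D, but conditional only on eligibility and fasting status |
| Evaluations complete before first injection | Protocol 10.1.1.1 | No; applies after the arm is confirmed, and only in the alirocumab arm |
| SAP default baseline | SAP 2.1.1 | No; gives way to the specific rule in 2.4.7 |
| Last value before randomization, covering Section 9.3 variables | Protocol 11.4.4 | Arguably yes, but 11.4.5 then states a different rule for the same variable |

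Both orders are consistent with the visit list and neither is required. Sections 11.4.4 and 11.4.5 also need to be reconciled.

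**2. What would a post-allocation baseline do?**

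Let d be the baseline difference between arms caused by disclosure, and β the slope of follow-up utility on baseline utility.

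- Adjusted contrast = (difference at follow-up) − β × (difference at baseline), so the shift is −β·d.
- Unadjusted change from baseline shifts by −d.

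The documents give neither d nor β. For assumed values, the size of β·d is:

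| d | β = 0.3 | β = 0.5 | β = 0.7 |
|---|---|---|---|
| 0.01 | 0.003 | 0.005 | 0.007 |
| 0.03 | 0.009 | 0.015 | 0.021 |
| 0.05 | 0.015 | 0.025 | 0.035 |

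The raw-change shift equals d, that is 0.01 to 0.05. If the form is completed before allocation, d = 0 and both shifts vanish.

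**3. Simulation check of the formula.** The check used 100 patients per arm, one follow-up time, an assumed utility SD of 0.15, no true effect and 2,000 runs per setting. With d = 0.02 the mean adjusted effects were −0.007, −0.010 and −0.014 for β = 0.3, 0.5 and 0.7 (formula −0.006, −0.010, −0.014). With d = 0.05 they were −0.015, −0.026 and −0.035 (formula −0.015, −0.025, −0.035).

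**4. How plausible is the upper end?** SAP 2.1.6 gives a utility range of −0.111 to 1 over five items with three levels, which is ten level steps: 1.111 / 10 ≈ 0.11 per step on average. A mean shift of 0.05 then needs a net 0.05 / 0.11 ≈ 45% of one arm to move by one level within the visit, and 0.01 needs about 9%. Actual item weights vary, so this is only a rough guide. It suggests that the lower rows of the table are unlikely.

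**The case against.** **Other text points to assessment first.** The early bullet is framed as notifying enrolment, and the bullet that actually instructs randomization comes after the EQ-5D and blood sampling. The lipid rule fits that order. Lipid baseline must be a central-laboratory value up to the time of randomization, and the first scheduled central-laboratory sample is the Visit 1 sample. This is a fair reading and may be what was intended. It stands as inference, because no sentence binds the EQ-5D to that order.

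**The two baseline rules may be compatible.** Only one EQ-5D is scheduled at Week 0, so the Visit 1 wording may simply name which assessment is used, with 11.4.4 supplying the timing. That is arguable for the Protocol. It does not help in the SAP, where the default yields to the specific rule.

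**Disclosure to the patient is not stated.** The text says the arm is communicated, without naming the patient. That the patient learns it at Visit 1 follows from the open-label design, the first injection and the arm-specific next appointments given there.

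**A clean baseline does not cure open-label reporting.** If a reporting effect d persists at follow-up, a pre-allocation baseline leaves the whole of d in the contrast, while a post-allocation baseline leaves d − β·d = (1 − β)·d. This stands: in that case total reporting bias is not reduced by the fix. A post-allocation baseline would, however, remove part of it only by accident and by an unknown amount.

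**The stakes are low.** EQ-5D is in no stated objective and outside the testing hierarchy (Protocol 11.4.2.3, SAP 2.4.4.3). The QOL population is analyzed by treatment actually received (SAP 2.3.3), so the contrast is not strictly a randomized one. This limits the weight of the point but does not remove it.

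**Conclusion.** The point holds as a gap in sequencing. The plan permits an EQ-5D baseline recorded after the arm is known, does not require one, and gives two baseline rules for the same variable.

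The size cannot be derived from the documents. It is −β·d in the MMRM: 0.003 to 0.035 utility units in size over the assumed ranges, with the upper end implausible, and zero if sites complete the form before allocation. These figures assume that disclosure shifts only the baseline and that β is the same at each visit; the planned baseline-by-time term lets it differ.

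Three stronger readings are tempting and not supported:

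- **That the baseline values are contaminated.** The second bullet order would give a pre-allocation value, and nothing shows which order sites followed.
- **That the bias could reverse the utility result.** This would need β·d to exceed the true difference, and the documents give none of these quantities.
- **That the trial's main conclusions are at risk.** The IVUS, lipid and safety results do not use this baseline.

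The gap is modest, but closing it costs very little.

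**What to change.** - **Protocol 10.1.1.1:** require the Visit 1 EQ-5D to be completed before the registration center is contacted for randomization, and make the two registration-center bullets consistent with that order.
- **Protocol 11.4.5 and SAP 2.4.7:** define baseline as the Visit 1 EQ-5D completed before randomization, in line with Protocol 11.4.4 and SAP 2.1.1.
- **Patients already enrolled:** keep their Visit 1 values in the main analysis. Where the order is unknown, add one sensitivity model of post-baseline utility without the baseline covariate. The response must be the utility itself, because the change score still contains the baseline.

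**Cost.** One line in the visit instructions, one line in each baseline definition, and one extra model run; no added visit or procedure. The sensitivity run loses precision. If baseline and follow-up SDs are equal, so that β is also the correlation, its standard error grows by about 1/√(1 − β²): 1.05, 1.15 and 1.40 for β = 0.3, 0.5 and 0.7. The main model keeps its precision. The change does not address knowledge of the arm at later EQ-5D visits, which should be stated when the results are reported.

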11.5 INTERIM ANALYSIS

No interim analysis is planned.

12 ETHICAL AND REGULATORY CONSIDERATIONS

12.1 ETHICAL AND REGULATORY STANDARDS

This clinical trial will be conducted by the Sponsor, the Investigator, and delegated Investigator staff and sub-Investigator, in accordance with consensus ethics principles derived from international ethics guidelines, including the Declaration of Helsinki, and the ICH guidelines for Good Clinical Practice (GCP), all applicable laws, rules and regulations.

This clinical trial will be recorded in a free, publicly accessible, internet-based registry, no later than 21 days after the first patient enrollment, in compliance with applicable regulatory requirements and with Sanofi public disclosure commitments.

12.2 INFORMED CONSENT

The Investigator (according to applicable regulatory requirements), or a person designated by the Investigator, and under the Investigator's responsibility, should fully inform the patient of all pertinent aspects of the clinical trial including the written information giving approval/favorable opinion by the ethics committee (IRB/IEC). All participants should be informed to the fullest extent possible about the study, in language and terms they are able to understand.

Prior to a patient's participation in the clinical trial, the written informed consent form should be signed, name filled in and personally dated by the patient or by the patient's legally acceptable representative, and by the person who conducted the informed consent discussion. A copy of the signed and dated written informed consent form will be provided to the patient.

If informed consent is obtained under special circumstances (emergency, from a guardian, minor, etc.), the method should be specified following the ICH requirements.

The informed consent form used by the Investigator for obtaining the patient's informed consent must be reviewed and approved by the Sponsor prior to submission to the appropriate ethics committee (IRB/IEC) for approval/favorable opinion.

The Investigator (according to applicable regulatory requirements), or a person designated by the Investigator, should fully inform the patient of all pertinent aspects of the clinical trial including the written information given approval/favorable opinion by the ethics committee (IRB/IEC). All participants should be informed to the fullest extent possible about the study in language and terms they are able to understand.

12.3 INSTITUTIONAL REVIEW BOARD/INDEPENDENT ETHICS COMMITTEE (IRB/IEC)

As required by local regulation, the Investigator or the Sponsor must submit this clinical trial protocol to the appropriate IRB/IEC, and is required to forward to the respective other party a

copy of the written and dated approval/favorable opinion signed by the chairman with IRB/IEC composition.

The clinical trial (study number, clinical trial protocol title and version number), the documents reviewed (clinical trial protocol, informed consent form, Package Insert, Investigator's curriculum vitae [CV], etc.) and the date of the review should be clearly stated on the written (IRB/IEC) approval/favorable opinion.

The IMP will not be released at the study site and the Investigator will not start the study before the written and dated approval/favorable opinion is received by the Investigator and the Sponsor.

During the clinical trial, any amendment or modification to the clinical trial protocol should be submitted to the health authorities (competent regulatory authority), as required by local regulation, in addition to the IRB/IEC before implementation, unless the change is necessary to eliminate an immediate hazard to the patients, in which case the health authorities (competent regulatory authority) and the IRB/IEC should be informed as soon as possible. They should also be informed of any event likely to affect the safety of patients or the continued conduct of the clinical trial, in particular any change in safety. All updates to the Investigator's Brochure or labeling information, will be sent to the IRB/IEC and to health authorities (competent regulatory authority), as required by local regulation.

A progress report is sent to the IRB/IEC at least annually and a summary of the clinical trial's outcome at the end of the clinical trial.

13 STUDY MONITORING

13.1 RESPONSIBILITIES OF THE INVESTIGATOR(S)

The Investigator is required to ensure compliance with all procedures required by the clinical trial protocol and with all study procedures provided by the Sponsor (including security rules). The Investigator agrees to provide reliable data and all information requested by the clinical trial protocol (with the help of the CRF, Discrepancy Resolution Form [DRF] or other appropriate instrument) in an accurate and legible manner according to the instructions provided and to ensure direct access to source documents by Sponsor representatives.

If any circuit includes transfer of data particular attention should be paid to the confidentiality of the patient's data to be transferred.

The Investigator may appoint such other individuals as he/she may deem appropriate as sub-Investigators to assist in the conduct of the clinical trial in accordance with the clinical trial protocol. All sub-Investigators shall be appointed and listed in a timely manner. The sub-Investigators will be supervised by and work under the responsibility of the Investigator. The Investigator will provide them with a copy of the clinical trial protocol and all necessary information.

